8.1.4 Inclusion/Exclusion Criteria

The study specific inclusion/exclusion criteria are presented in Section 8.1 and Section 8.2 of the protocol.

8.1.5 Subject Enrollment and Disposition

As previously described, Study 3005 is an extension study. Subjects will be assigned to an enrollment cohort based on the study in which they received their first LCIG infusion. Due to the similarity in study design, Study 3001 and Study 3002 will be considered a single enrollment cohort. The number and percentage of subjects in each of the following enrollment cohorts will be summarized:

- Subjects who received their first LCIG infusion in Study S187.3.001 or Study S187.3.002
- Subjects who received their first LCIG infusion in Study S187.3.003
- Subjects who received their first LCIG infusion in Study S187.3.004

Subjects are expected to continue in the study until commercial LCIG becomes available to them. If commercial LCIG becomes available to a subject, a final visit shall be scheduled and the subject will be regarded as having completed the study if they complete this final visit. If at any time after providing informed consent, a subject prematurely discontinues their participation in the study, the primary reason for premature discontinuation shall be recorded on the "Study Termination" CRF. The primary reason can include one of the following:

- Adverse Event
- Lack of Efficacy
- Lost to Follow-up
- Withdrew Consent
- Administrative
- Protocol Violation

Premature discontinuations will be summarized by 3005 treatment year after allocating each premature discontinuation to a 3005 treatment year based on the study day of the subject's last dose date and the study day intervals described in Section 6.4.9.

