1.2 Synopsis

Name of Sponsor: AbbVie	Protocol Number: S187.3.005
Name of Finished Product: Levodopa-Carbidopa Intestinal Gel (LCIG) 20 mg/mL - 5 mg/mL	Phase of Development: 3
Name of Active Ingredient: Levodopa-Carbidopa	Date of Protocol Synopsis: 17 December 2013
Protocol Title: Open-Label Continuation Treatment Study with Levodopa-Carbidopa Intestinal Gel in Subjects with Advanced Parkinson's Disease and Severe Motor-Fluctuations Who Have Exhibited a Persistent and Positive Effect to Treatment in Previous Studies	
Study Center(s) (Planned): Approximately 70	
Study Duration: The protocol duration is planned until the finished product is available commercially in the respective countries where subjects are participating in the study. The expected protocol duration will continue through successful NDA and subsequent approval (approximately 4 years). The protocol duration will be extended 4 years in the UK from the approval date of Amendment 3.01. If it is deemed necessary to continue treatment after 4 years in the UK, either an amendment will be made to the current protocol or a new protocol will be submitted.	
Objectives: The primary objective is to provide continued access to subjects who would like to continue Levodopa-Carbidopa Intestinal Gel (LCIG), after completion of an open-label study (S187.3.003 or S187.3.004). The secondary objectives are to assess the long-term safety and tolerability of the LCIG therapeutic system, and to assess the maintenance of efficacy using data collected from US subjects.	
Methodology: This is a Phase 3B, open-label, multi-center, study. Subjects will be provided with LCIG, if judged medically indicated and if it is not commercially available. Data collected will be for evaluation of safety and efficacy, and for periodic assessment of the continued appropriateness of the subject's participation in the study. The decision to continue is based on the Principal Investigator's clinical judgment.	
Number of Subjects (Planned): It is anticipated that approximately 275 subjects who had participated and completed one of the open-label LCIG clinical trials will be eligible for this continued treatment with LCIG, until it is commercially available.	

Diagnosis and Main Criteria for Inclusion:

In order to be eligible to participate in this study, subjects must meet the following criteria:

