In countries where LCIG is not commercially available, the treatment will be made available to subjects who complete participation in either LCIG open-label Study S187.3.003 or S187.3.004. Such product will be made available by the Sponsor in accordance with all local regulations as long as such is warranted by the therapeutic benefit. The latter will be determined in consultancy with the responsible neurologist, the subject and the Sponsor. Subjects who continue to receive study drug will be evaluated at least semi-annually by the Investigator. In cooperation with the investigational site, all necessary support will be provided by the Sponsor's local representatives.

Reference Therapy, Dose and Mode of Administration:

Not applicable.

Criteria for Evaluation:

Safety and Tolerability Assessments:

Safety will be assessed by:

- Physical examination, including weight
- Neurological examination
- Vital signs
- Resting ECGs
- C-SSRS
- Clinical laboratory assessments including biochemistry, hematology, urinalysis, and special labs to monitor for vitamin deficiencies
- Concomitant medication usage
- Adverse event monitoring (including sleep attacks, development of impulsive behavior and of melanoma)
- Monitoring complications of the infusion device

Tolerability will be assessed by the number of subjects who complete the study.

Efficacy Assessments at US Sites Only:

- Parkinson's Disease Diary[®] assessment of motor state completed for the 3 consecutive days prior to each clinic visit
- The Unified Parkinson's Disease Rating Scale (UPDRS)
- Parkinson's Disease Questionnaire-39 (PDQ-39)

Statistical Methods:

The primary statistical objective of this study will be to evaluate the long-term safety of LCIG.

Safety Population:

The Safety Population includes all subjects who have taken at least one dose of study medication in this study.

Efficacy Population:

The Efficacy Population includes all subjects at US sites who have taken at least one dose of study medication in this study and have at least one efficacy assessment in this study.

Safety:

The safety population will be used for the analysis of the safety and tolerability data.

Safety will be evaluated using adverse events (AEs), complications of the infusion device, and changes in laboratory parameters, electrocardiograms, vital signs, C-SSRS and the Minnesota Impulsive Disorders Interview (MIDI).

Statistical Methods (Continued):

Efficacy:

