The final visit in the previous open-label LCIG study will provide baseline assessments for the S1878.3.005 study. Subjects will be reassessed every 6 months for the appropriateness of the continuation of treatment with LCIG. If the subject is deemed inappropriate for continued treatment by the Investigator, the subject would be discontinued from treatment and the PEG-J will be removed, with a follow-up visit

occurring 1 week later. For subjects who elect not to continue LCIG treatment, the PEG-J will be removed, and a follow-up clinic visit will occur 1 week later.

Safety assessments should include physical examination, neurological exam, orthostatic vital signs, weight, adverse event monitoring, assessment of impulsive behavior and sleep attacks, melanoma check, electrocardiogram (ECG), clinical hematology, biochemistry, special labs to monitor for vitamin deficiencies, and urinalysis.

The following efficacy assessments will be completed at US sites:

- Parkinson's Disease Diary[®] assessment of motor state completed for the 3 consecutive days prior to each clinic visit (excluding the drug dispensation visits),
- Unified Parkinson's Disease Rating Scale (UPDRS), and
- Parkinson's Disease Questionnaire-39 (PDQ-39).

At each visit, complications or adverse events with the infusion device (i.e., the tubing system and the pump) will also be recorded and reported. Tube placement will be checked by radiography if there is a clinical indication that the tube has been displaced. The tube will be repositioned, if needed, to the original placement site just beyond the ligament of Treitz. At each visit the tube insertion site, including the stoma, will also be inspected. On a yearly basis, at a minimum, an assessment will be made of the need for a replacement of the PEG-J. The frequency of replacement should be in accordance with local practice.

The protocol duration is planned until the finished product is available commercially in the respective countries where subjects are participating in the study. The expected protocol duration will continue through successful NDA and subsequent approval (approximately 4 years). ***The protocol duration will be extended 4 years in the UK from the approval date of Amendment 3.01. If it is deemed necessary to continue treatment after 4 years in the UK, either an amendment to the current protocol will be made or a new protocol will be submitted.***

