7.2 Secondary Objectives

To assess the long-term safety and tolerability of the LCIG therapeutic system by the following:

- Physical examination, including weight
- Neurological examination
- Vital signs
- Resting ECGs
- Clinical laboratory assessments including biochemistry, hematology, urinalysis, and special labs to monitor for vitamin deficiencies
- Concomitant medication usage
- Adverse event monitoring, including for the development of sleep attacks, melanoma, or excessive impulsive behavior
- Monitoring complications of the infusion device
- Tolerability assessed by number of subjects who complete the study

To assess the maintenance of efficacy using the following data collected from US subjects:

- Off time, On time with troublesome dyskinesia, and On time without troublesome dyskinesia as measured by the Parkinson's Disease Diary
- UPDRS total score, Parts I, II, III and IV scores, and dyskinesia item score
- PDQ-39 summary index and domain scores

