9.1 Subject Disposition

Subject disposition (DS) will be summarized for all centers/countries combined by means of the default summary statistics described in Section 6.0 (General Definitions, Methods, Naming Conventions and Data Handling).

Subject Samples:	Tables	All subjects consented and Efficacy Sample US Subset
	Listings	All subjects consented
	Figures	Not applicable
Subgroups:		Not applicable
Abbreviation:		DS

Standard Presentations

- DST001 The primary reason for premature discontinuation after consent, as recorded on the "Study Termination" form, will be presented. The primary reason for premature discontinuation includes:
- Adverse Event
 - Lack of Efficacy
 - Lost to Follow-up
 - Withdrew Consent
 - Administrative
 - Protocol Violation

The number of subjects who have completed the study and the number whose participation in the study is ongoing will also be presented. The percentage of subjects will be calculated relative to the number of consenting subjects.

- DST002 Subject validity/subject sample status will be summarized with the reason for exclusion from the Safety sample. The only reason for exclusion from the safety sample will be that the subject did not infuse any study medication after providing informed consent.
- DST003 The number and percentage of subjects prematurely discontinuing in each 3005 treatment year will be summarized.

Standard subject data listings include:

- DSL001 A listing of subjects who prematurely discontinued their participation in the study prior to receiving 3005 LCIG.

DSL002 A listing of subjects who discontinued participation after receiving 3005 LCIG will be presented. The relative treatment day of last contact with the subject and the last day of 3005 LCIG infusion, as captured on the "Study Termination" CRF form will be calculated as:

- Relative Treatment Day of Last Contact = (Date of Last Contact – Date of First 3005 LCIG Infusion) + 1
- Relative Treatment Day of Last 3005 LCIG Infusion = (Date of Last 3005 LCIG Infusion – Date of First 3005 LCIG Infusion) + 1

DSL003 Exclusion from the Safety subject sample together with the reason(s) for exclusion will be presented. This listing will include all possible reasons for exclusion per subject.

Study Specific Presentations

Not applicable.

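### The completer count used for tolerability depends on when commercial LCIG arrives as well as on discontinuation, so it cannot be read as tolerability on its own

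*SAP*

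**What the plan says.** The synopsis (Protocol 1.2) states: "Tolerability will be assessed by the number of subjects who complete the study". SAP 7.2 carries the same measure as the last item of its safety and tolerability list: "Tolerability assessed by number of subjects who complete the study". Protocol 6.2 has the equivalent item.

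Completion is defined in SAP 8.1.5. "Subjects are expected to continue in the study until commercial LCIG becomes available to them". When that happens a final visit is scheduled, and "the subject will be regarded as having completed the study if they complete this final visit". Protocol 7.1 sets the end of the study the same way: "The protocol duration is planned until the finished product is available commercially in the respective countries". The synopsis expects about 4 years (with a separate UK extension), and the visit labels in SAP Table 1 run to Month 84. No common follow-up length per subject is fixed.

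For reporting, SAP 9.1 plans DST001 (reasons for premature discontinuation, with completed and ongoing subjects shown separately, as percentages of consenting subjects) and DST003: "The number and percentage of subjects prematurely discontinuing in each 3005 treatment year will be summarized".

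**The concern.** A count of completers reads naturally as the number of subjects who tolerated treatment to the end. Here the end is an external event. Two groups with the same yearly discontinuation risk will show different completer shares if commercial product reaches them at different times, and two groups with different risks can show the same share.

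Some exits that lower the count also have nothing to do with tolerability. Protocol 9.0 files relocation under withdrawn consent and sponsor decisions under administrative reasons.

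Long-term tolerability is a stated secondary objective. If the clinical study report answers it with the completer count, the reader cannot tell how much of the figure reflects the product and how much reflects the launch calendar.

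**Working it through.** The documents give no expected completion figure, discontinuation rate or power calculation, so there is no planned figure to reproduce. The planned 275 subjects are an anticipated rollover number. Every rate and launch time below is an assumption, used only to show how the measure behaves.

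**1. Same yearly risk, different launch time.** With a constant yearly discontinuation probability d and launch t years after entry, the completer share is (1 − d)^t.

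| d | t = 1 | t = 3 | t = 5 |
|---|---|---|---|
| 0.10 | 0.90 = 90% | 0.90³ = 73% | 0.90⁵ = 59% |
| 0.15 | 0.85 = 85% | 0.85³ = 61% | 0.85⁵ = 44% |

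**2. Different risk, same count.** With a constant hazard h per year and N = 275, expected completers are 275 × exp(−hT).

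- h = 0.05, T = 4; h = 0.10, T = 2; and h = 0.20, T = 1 all have hT = 0.20.
- Each gives 275 × exp(−0.20) = 225 completers (81.9%), across a fourfold range of hazard.

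**3. Same launch time, different risk.** At T = 4, h = 0.05, 0.10, 0.15 and 0.20 give 225, 184, 151 and 124 completers. The count does respond to discontinuation when launch time is held fixed.

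**4. An interim cut.** Suppose half of 275 subjects reach launch at year 1 and half at year 4, with h = 0.10 and a data cut at year 3.

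- Completers: 137.5 × exp(−0.10) = 124 (45.2%).
- Ongoing: 137.5 × exp(−0.30) = 102.
- Discontinued: 275 − 124 − 102 = 49.

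None of the 102 ongoing subjects can be a completer yet.

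**5. A measure that accounts for time at risk.** With h = 0.10, discontinuations over subject-years are 26/262 at T = 1, 50/498 at T = 2, 91/907 at T = 4 and 138/1384 at T = 7. Each is 0.10 per year. Over the same launch times the completer share falls from 90.5% to 81.9%, 67.0% and 49.7%.

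**6. Denominators in the SAP.** The yearly tables for concomitant antiparkinsonian medication (8.2.4), adverse events (8.5.1) and device complications (8.5.5.1) each state who is at risk in a given year. For DST003, neither 8.1.5 nor 9.1 does; 8.1.5 says only that a discontinuation is allocated to a year by the study day of the last dose.

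**The case against.** The strongest reply is that a reader of the report is not left with the completer count alone.

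- Protocol 6.2 and SAP 7.2 list adverse events, device complications, laboratory tests and other items jointly under safety and tolerability.
- DST001 gives discontinuation by reason, including adverse event and lack of efficacy. AET005 tabulates events leading to discontinuation. DSL002 lists the relative day of last infusion for each subject who discontinued.
- EXT001 gives the number exposed in each yearly interval and total subject-years, so approximate yearly proportions and rates could be worked out by hand.
- The study is single-arm, alpha is not applicable, and no decision rests on the count.

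All of this stands, and it limits the point. It does not remove it: no planned table presents a cumulative risk, DST003 has no stated denominator, and none of these tables is designated as the answer to the tolerability objective.

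Four stronger readings are tempting, and the documents do not support them.

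- A reader might infer that the count reflects launch date instead of tolerability. It does not: a completer must not have discontinued first, and step 3 shows the count falling as risk rises.
- A reader might infer that tolerability has no other measure. The synopsis names completers alone, but the objectives sections list other items jointly.
- A reader might infer that early-launch and late-launch countries will be compared. SAP 9.1 pools all centers and countries with no subgroups, so launch timing enters through the pooled figure.
- A reader might infer that ongoing subjects are mishandled at the interim. DST001 shows them as a separate category, which is appropriate, and no cutoff applies to the final report.

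**Conclusion.** The point holds in a limited form. The completer count depends jointly on when commercial LCIG becomes available and on discontinuation, and cannot separate them. It therefore cannot be interpreted as tolerability by itself, least of all at the interim with its 30 September 2015 cutoff.

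Under the assumed 10% yearly risk, moving launch from 1 to 5 years moves the share from 90% to 59% with no change in tolerability. These sizes rest on a constant rate and on launch times that the documents do not give. The dependence on launch timing follows from the definition in SAP 8.1.5 and does not rest on them. The remaining gap in the analysis is specific: no cumulative estimate, and no at-risk denominator for DST003.

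**What to change.** In the Safety sample:

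1. Summarise tolerability by a Kaplan-Meier estimate of time from Day 1 (RFSTDTN) to premature discontinuation for any reason. Censor at transfer to commercial product (completion) or, at the interim, at the Cutoff Date.
2. For discontinuation due to an adverse event, use cumulative incidence with all other premature discontinuations as competing events. Censoring them and reporting one minus Kaplan-Meier would overstate the risk.
3. Give 95% confidence intervals for both estimates at each 3005 treatment year.
4. State the DST003 denominator as the subjects whose last 3005 LCIG infusion falls within or after the year's day range. SAP 8.2.4 already uses this rule for concomitant medication, and it matches the allocation of discontinuations by last dose date.
5. Keep the completer count as disposition only.

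The Kaplan-Meier estimate assumes that transfer, which is driven by product availability, is unrelated to a subject's later risk of discontinuing. The table note should say so.

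The cost is one extra table or figure. Day 1 comes from the first dispensing date in the DA panel, with the DM visit date as fallback. Last infusion and discontinuation or completion dates are in the DS panel, and the reason is on the Study Termination form. SAP 6.4.1 already derives the duration from these dates. No new data are needed, so this is a free improvement.

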8.2 Subject Characteristics

8.2.1 Demographic Data

Standard demographic data collected includes:

- Date of Birth
- Gender
- Race (American Indian or Alaska native, Asian, black of African heritage or African American, native Hawaiian or other Pacific Islander, or white)
- Ethnicity (Hispanic or Latino)
- Country

Age (years) will be derived in SAS[®] using Date of Birth, and calculated relative to Day 1, as follows:

$$\text{Age (years)} = \text{Day1_Y} - \text{Birth_Y} - (0 < \text{Day1_M} < \text{Birth_M OR} \\ [\text{Day1_M} = \text{Birth_M AND } 0 < \text{Day1_D} < \text{Birth_D}])$$

Where:

Day1_D: Day of Day 1 date.

Day1_M: Month of Day 1 date.

Day1_Y: Year of Day 1 date.

Birth_D: Day of Birth.

Birth_M: Month of Birth.

Birth_Y: Year of Birth.

Where the Date of Birth is incomplete the following convention will be used:

- Where the day is missing and month and year are available the day will be completed as the 15th. For example, Date of Birth specified as – JAN1980 will be completed as **15JAN1980**.
- If the day and month are missing and the year is available the day and month will be completed as 02JUL (the 183rd day of the year). For example, Date of Birth specified as – 1980 will be completed as **02JUL1980**.

8.2.2 Other Baseline Characteristics

Other Baseline characteristics include:

Vital Signs:

- Height (m) as measured during the Initial Screening Period
- Weight (kg)
- BMI (kg/m²)
- Body Temperature (degrees Celsius) including route of measurement
- Systolic Blood Pressure (SBP [mmHg]) supine, standing and orthostatic
- Diastolic Blood Pressure (DBP [mmHg]) supine, standing and orthostatic
- Pulse Rate (beats per minute [bpm]) supine, standing and orthostatic

Study specific calculations and/or conversions include:

Height (m): If applicable, height will be converted from inches to meters for the calculation of Body Mass Index (BMI), using the following formula:

$$\text{Height (m)} = (\text{XX inches} * 2.54)/100 \text{ and presented to two decimal precision.}$$

Weight (kg): If applicable, weight will be converted from pounds to kilograms for the calculation of BMI, using the following formula:

Weight (kg) = (XX pounds * 0.4536) and presented to one decimal precision.

Body Mass Index calculated as:

BMI (kg/m²) = Weight (kg)/Height (m)² and presented to one decimal precision.

Temperature (degrees Celsius): If applicable, temperature will be converted from degrees Fahrenheit to Celsius, using the following formula:

Temperature (degrees C) = (XX degrees F – 32)/1.8 and presented to one decimal precision.

8.2.3 Medical History and Other Disease History

8.2.3.1 Medical History

Medical history (MH) is defined as any condition, with the exception of the study indication, that the subject reported during the Initial Screening Period. Medical history will include findings reported on either the medical history or neurological history CRF.

Medical history findings will be coded using the Medical Dictionary for Regulatory Activities (MedDRA),² Version 14.0 or later and will be presented by primary System Organ Class (SOC) and by Preferred Term (PT) within SOC. The SOCs and PTs will be sorted alphabetically at each coded level. Medical history will be reported on a by-subject basis. This implies that if the subject reported the same condition (conditions mapped to the same PT) repeatedly, the condition will only be counted once. The earliest date will be regarded as the start date of the condition and the last available date, as the stop date of the condition.

Missing or partial dates for medical history will not be completed, for example, if only a month and year are available as – FEB2005, the day will not be imputed in order to

complete the date. If "End Date" information is not available it will be assumed that the finding is "Ongoing" at the time of enrollment in the study.

